# 3 Study Design

This study is a non-randomized, observational, phase IV, multi-site pilot study to investigate the compliance with and perceptions of treatment, as well as HRQOL in surgically resected melanoma patients undergoing HDI or PEG IFN therapy. After discussion with their treating physician, patients will receive 1 of 2 approved adjuvant therapies for melanoma:

- 1. Cohort A: high-dose interferon alfa (HDI, Intron® A)
- 2. Cohort B: pegylated alfa-interferon 2b (PEG IFN, SylatronTM)

Although the study is not randomized, in order to attempt to discern a difference between the groups, a maximum of a 60:40 split will be allowed on the protocol. This means that a

maximum of 60% of patients will be permitted on either arm and if achieved, that particular arm will be capped at 60%.

Each treatment arm will have a pretreatment phase (within 4 weeks/28 days of starting the induction phase (4 weeks of HDI or 8 weeks of PEG IFN), a maintenance phase (treatment administration at specified times up to 1 year), and an end-of-study assessment, conducted within 21 days of discontinuation of study treatment.

The primary endpoint of this study is to compare compliance with treatment of HDI and PEG IFN. Patients will complete drug administration diaries to track compliance with the recommended dosing schedule. Secondary endpoints include comparing treatment perceptions and HRQOL between treatment groups, comparing the frequency of Grade 3 and Grade 4 adverse events (AEs) in each treatment arm, and evaluating the reasons for patients' choice of treatment with HDI or PEG IFN through the use of the Interferon Preference Questionnaire

Patients receiving HDI will complete the CCSQ and FACT-BRM at baseline, every 2 weeks during the induction phase and monthly during the maintenance phase (beginning at Day 29) for up to 1 year. Patients receiving PEG IFN will complete the CCSQ and FACT-BRM at baseline, 2 weeks, 4 weeks, 6 weeks, and monthly during the maintenance phase (beginning at Day 57) for up to 1 year. Adverse events will be monitored throughout the study. Any dose adjustments based on toxicities will be made according to investigator judgment and the package insert for each product. Patients will also be queried to determine the most important reasons for choice of treatment with HDI versus PEG IFN.

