### 9 Data Analysis

This is an observational pilot study with no formal sample size calculation based on a previously established effect size. For both primary and secondary outcomes, descriptive data will be presented (i.e., means and standard deviations or medians and interquartile ranges for interval and ordinal data as appropriate; frequencies and percentages for nominal/categorical data). Missing data will not be imputed due to the study's exploratory nature; however, all missing data points will be recorded and assessed for possible response patterns.

Selected inferential analyses will be conducted for exploratory purposes using estimated clinically important between-group differences. The study authors will seek to maintain at least a 60:40 between-group ratio to guard against unequal variance.

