#### Primary outcome

• To compare compliance with HDI and PEG IFN (percentage of doses taken as recorded in patient diaries), with a 30% between-group difference deemed clinically relevant, a mixed randomized-repeated measures analysis of variance (ANOVA) will be conducted with treatment group (HDI versus PEG IFN) as the randomized (between-group) factor and treatment period time as the repeated measures (withingroup) factor. For the repeated measures factor of time, given the different induction phases for the two regimens (i.e., approximately 4 weeks for HDI versus 8 weeks for PEG IFN), the ANOVA will capture outcomes at baseline, 2 weeks, 3 months, 6

months and 12 months, with inclusion of the latter outcome dependent on the amount of missing data.

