#### 9.3 Sample Size Calculation

Due to the pilot study design, minimum sample size has not been calculated formally. The sample size of 100 patients is expected to generate data adequate to determine if a larger trial is warranted.

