Data Analysis -REVISED JULY 2023

Due to the study's pilot study design, sample size was not calculated formally. For both primary and secondary outcomes, descriptive data are presented (i.e., medians and ranges for continuous data, frequencies and percentages for categorical data).

Although the original data plan called for exploratory mixed randomized-repeated measures analysis of variance (ANOVA) to be conducted for the primary and two secondary outcomes, the pattern of missing data across patients at the designated time points was too prevalent (and appeared not to be missing at random) to ensure robust ANOVA results. Therefore, we reported separate non-parametric statistical outcomes when deemed feasible (i.e., adequate and balanced subgroup sample sizes) in an attempt to obtain as much information as possible about data trends and patterns. Because we were unable to capture within-subject correlations over time, as well as the treatment group*time interaction, our results should be interpreted accordingly.

The primary outcome was compliance with HDI and PEG IFN (i.e., percentage of doses taken based on total doses required over 53 weeks, as recorded in patient diaries), with a difference of 30% between groups deemed clinically relevant. We reported frequencies and percentages per week and an overall percentage of doses taken at the end of 53 weeks, with statistical analysis of this outcome.

Secondary outcomes were as follows (with different time points reported depending on the highest outcome frequencies):

- Comparison of the convenience and satisfaction with chemotherapy for patients on standard HDI versus PEG IFN using a chemotherapy convenience and satisfaction questionnaire (CCSQ), summation of items CS1 – GP5, with a 30% between-group difference deemed clinically relevant. Time points of comparison were baseline/week 1, week 3, week 13, week 25, and week 50.
- Item GF7, which assesses contentment with current quality of life, at baseline/week 1, week 3, week 13, week 25, and week 49.
- Item CS10, which assesses satisfaction with current results of chemotherapy, at week 1, week 3, week 13, week 25, week 37, and week 45.
- Items CS11 and CS12, which measure recommendation/choice of chemotherapy regimen, at week 1, week 3, week 13, week 25, week 37, and week 45.
- Item CS13, which rates the chemotherapy regimen overall, at week 1, week 3, week 13, week 25, week 37, and week 45.

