- Treatment-related side effects that may impact the patient's health-related QoL (HRQOL) using the Functional Assessment of Cancer Therapy of Biologic Response Modifier (FACT BRM), with a 30% between-group difference in scores deemed clinically relevant. Time points of comparison were baseline/week 1, week 3, week 13, week 25, and week 50.

- The frequency of Grade 3 and 4 adverse events (AEs), according to the National Cancer Institute (NCI) Common Toxicity Criteria for Adverse Events (CTCAE) for patients on standard HDI versus PEG IFN, and the frequency of severe adverse events (SAEs), regardless of grade.
- Patients' reasons for their choice of treatment with HDI versus PEG IFN at the study's conclusion, for those cases in which patients were presented with a choice of either treatment option.

All analyses were conducted using IBM SPSS Statistics for Windows, Version 25.0 (Armonk, NY: IBM Corp.), with $p < .05$ denoting statistical significance.

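### Testing only where subgroups are balanced lets differential dropout select which comparisons are tested; the 60:40 cap limits, but does not remove, the effect of unequal variance

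*Protocol*

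**What the plan says.** Two statements bear on group balance. They come from different documents and serve different purposes.

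- **Protocol, section 9 (Data Analysis):** "The study authors will seek to maintain at least a 60:40 between-group ratio to guard against unequal variance." The planned analysis there is "a mixed randomized-repeated measures analysis of variance (ANOVA) will be conducted with treatment group (HDI versus PEG IFN)" as the between-group factor; no unequal-variance version is named. Section 3 (Study Design) states the same limit as an enrolment rule, "a maximum of a 60:40 split will be allowed on the protocol", and gives a different reason for it: to help discern a difference between the groups.
- **SAP (revised July 2023):** the ANOVA is abandoned because missing data were too common and did not look random. Unnamed non-parametric tests replace it, run "when deemed feasible (i.e., adequate and balanced subgroup sample sizes)". No number defines adequate or balanced. Time points for the secondary outcomes are chosen by where most outcomes were recorded. Significance is declared "with $p < .05$ denoting statistical significance".

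Three further statements set the limits of the point. The SAP presents descriptive data for all primary and secondary outcomes. Its sentence on the overall 53-week compliance figure promises a statistical analysis and attaches no balance condition. Protocol section 5.4.1 ends all study procedures once interferon is permanently discontinued.

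**The concern.** A condition for testing that depends on the numbers left in each arm is not neutral here. Those numbers depend on who stopped interferon, and stopping is closely tied to compliance and toxicity, which the study sets out to compare. Visits where the arms differ most in dropout are the least likely to be tested, and no stated threshold lets a reader check why a given comparison has a p-value and another does not.

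The Protocol's reason for the 60:40 limit is a separate weakness. A ratio of group sizes does not change either arm's variance. It only changes how far unequal variances disturb a test that assumes they are equal. The cap also applies at enrolment, so it does not fix the ratio among patients with data at later visits.

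**Working it through.** **Inputs.** N is 100 and the worst permitted enrolment split is 60:40 (Protocol sections 9.3 and 3). Alpha is 0.05 (SAP), taken as two-sided. The only retention figure is that over 60% of HDI patients complete a year (Protocol section 1.1). Neither document gives an SD, a variance ratio, PEG IFN retention or a threshold for balance, so these are assumed and shown as ranges. The sample size rests on "no formal sample size calculation based on a previously established effect size", so there is no stated figure to reproduce.

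**1. Is balance needed for a rank test?** The smallest attainable exact two-sided p is 2/C(n1+n2, n1).
- 30 v 10: 2/C(40,10) = 2/847,660,528 = 2.4e-9.
- 10 v 3: 2/C(13,3) = 2/286 = 0.007.

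Even strong imbalance leaves a usable test. This shows feasibility, not power or freedom from bias.

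**2. How strongly could dropout select the tests?** Assume a visit is tested if the remaining patients are within 60:40 with at least 10 per arm. Exact binomial probabilities:

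| Start | Retention, arm 1 / arm 2 | P(tested) |
|---|---|---|
| 50/50 | 60% / 60% | 0.985 |
| 50/50 | 60% / 40% | 0.51 |
| 50/50 | 60% / 30% | 0.11 |
| 60/40 | 60% / 60% | 0.52 |
| 60/40 | 60% / 40% | 0.03 |
| 60/40 | 40% / 60% | 0.95 |

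With the starting split held fixed, retention per arm largely decides whether a test is run.

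**3. What does 60:40 do under unequal variance?** For a pooled test with equal means, type I error is approximately 2[1 − Φ(t_crit·√(P/V))], where P = {[(n1−1)s1² + (n2−1)s2²]/(n1+n2−2)}·(1/n1+1/n2) and V = s1²/n1 + s2²/n2. For n = 60 and 40 with SDs 1 and 2:
- P = [(59·1 + 39·4)/98]·(1/60 + 1/40) = 2.194·0.04167 = 0.0914.
- V = 1/60 + 4/40 = 0.1167.
- √(P/V) = 0.885; 1.984·0.885 = 1.757; error = 0.079.

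At 50:50 with the same SDs, P = V = 0.1 and there is no inflation.

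Simulated rejection rates at 60:40 (normal data, equal centres; 20,000 runs per setting, 10,000 for ratio 1.25):

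| SD ratio | Smaller arm more variable: pooled / rank-sum | Larger arm more variable: pooled / rank-sum |
|---|---|---|
| 1.25 | 6.3% / 5.7% | 3.8% / 4.2% |
| 1.5 | 7.1% / 6.2% | 3.6% / 4.4% |
| 2 | 8.4% / 7.6% | 2.9% / 4.3% |
| 3 | 10.1% / 9.3% | 2.4% / 4.7% |

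Welch and Brunner-Munzel stay at about 5% (4.8-5.3%) in all these settings. The rank-sum figures apply when the test is read as a comparison of centres. At exactly 50:50 with SD ratio 3, rank-sum still rejects 6.8%, so balance does not fully protect that test.

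**4. How much does the cap help?** Pooled test, SD ratio 2, smaller arm more variable: 4.9% at 50:50, 8.4% at 60:40, 12.4% at 70:30 and 18.2% at 80:20. The cap prevents much of the possible inflation.

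**The case against.** The strongest reply is that the variance argument targets an analysis no longer run. The 60:40 sentence supported the ANOVA, and the SAP offers balance as a feasibility criterion, not as protection against unequal variance. That stands, and the two parts must be kept apart.

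A reader might infer that 60:40 gives no protection. Step 4 shows that it does, in part.

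A reader might also infer that unequal spread is built in, because a PEG IFN week has one dose and an HDI week three or five. That may matter for single-week percentages. The SAP's overall test is on the 53-week total, with about 53 weekly PEG IFN doses against 5×4 + 3×48 = 164 HDI doses, where this granularity almost disappears. With the same assumed stopping pattern in both arms, the simulated SD ratio of the total was only 1.05-1.07. CCSQ and FACT-BRM use the same scales in both arms. Ratios of 2 or 3 therefore remain assumptions, and the direction of any inequality is unknown.

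Larger error rates can be produced for badly unbalanced late visits, but the SAP's own condition would probably leave those untested, so both harms cannot be claimed for the same visit.

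Finally, inference is labelled exploratory and the SAP tells readers to interpret results with its limitations in mind. That lowers the stakes, although the SAP still declares significance at 0.05. None of this answers the point about an undefined, data-dependent condition for testing.

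**Conclusion.** The concern holds in two limited parts.

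First, the SAP's condition has no threshold, is applied with the data in view, and is not needed for a valid rank or Welch test. Since data collection follows treatment, it selects comparisons for testing on differential dropout. The probabilities from 0.985 down to 0.11 illustrate this under an assumed threshold and assumed retention; they do not estimate what happened. It would go too far to say that dropout decides what is reported: descriptive results are given for every outcome, and the overall 53-week compliance sentence carries no such condition.

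Second, the Protocol's cap limits the effect of unequal variance without removing it. At 60:40, nominal 5% becomes about 6-10% (pooled) or 6-9% (rank-sum) if the smaller arm is the more variable by an SD ratio of 1.25 to 3, and falls below 5% if the larger arm is. The documents do not support a claim that the trial's p-values are in fact too small.

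This is a worthwhile correction to an exploratory analysis; it does not invalidate the study.

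**What to change.** - **Protocol section 9:** say that the enrolment cap limits the effect of unequal variance, in place of saying that it guards against it.
- **SAP:** remove balance as a condition for testing. For each outcome with planned inference (compliance, the CCSQ CS1 to GP5 sum, the FACT-BRM sum), report n per arm and an effect estimate with 95% CI at every Protocol time point, including 12 months, whatever the counts. Compliance has no meaningful baseline value. Name a method valid under unequal spread, for example Welch for means or Brunner-Munzel for ordered scores, and label the results exploratory.
- **Limitation to state:** this removes selective testing. It does not remove the bias from comparing only patients still on treatment.

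The cost is some re-analysis of existing data, because the SAP describes completed work, and wide intervals at late visits. No new data are needed.

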#### Primary outcome

• To compare compliance with HDI and PEG IFN (percentage of doses taken as recorded in patient diaries), with a 30% between-group difference deemed clinically relevant, a mixed randomized-repeated measures analysis of variance (ANOVA) will be conducted with treatment group (HDI versus PEG IFN) as the randomized (between-group) factor and treatment period time as the repeated measures (withingroup) factor. For the repeated measures factor of time, given the different induction phases for the two regimens (i.e., approximately 4 weeks for HDI versus 8 weeks for PEG IFN), the ANOVA will capture outcomes at baseline, 2 weeks, 3 months, 6

months and 12 months, with inclusion of the latter outcome dependent on the amount of missing data.

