#### 5 Treatments

#### 5.1 Identity of Investigational Product

Patients will be offered HDI and PEG IFN and, after discussion with their treating physician, will initiate the therapy of their choice (Table 1). The HDI and PEG IFN dose may modified per institutional dosing guidelines.

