#### 6.7.1 CCSQ

The CCSQ is a questionnaire for oncology patients used to evaluate their overall satisfaction with and preferences for chemotherapy. The CCSQ was generated from interviews with 70 oncology patients, 7 oncologists, 4 nurses, and focus groups of 14 nurses. Interviews took place in the US, the United Kingdom, and France and were qualitatively analyzed. The CCSQ was designed for adults with a wide range of cancer types and stages and contains 21 items and 7 domains:

- 1. Expectations of chemotherapy
- 2. Feelings about side effects
- 3. Oral chemotherapy compliance
- 4. Convenience
- 5. Satisfaction with chemotherapy
- 6. Stopping chemotherapy
- 7. Reasons for non-compliance

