#### 6.8 Treatment Compliance

Patients will complete drug administration diaries to track compliance with the recommended dosing schedule. These diaries will also capture the onset of AEs in relationship to the day of drug administration. The diaries will be returned to the Investigator at the subsequent visit.

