#### 7.1 **Adverse Events**

An adverse event is the appearance or worsening of any undesirable sign, symptom, or medical condition occurring after starting the treatment even if the event is not considered to be related to the treatment. Treatment includes the investigational drug under evaluation and the comparator drug or placebo that is given during any phase of the study. Medical conditions/diseases present before starting treatment are only considered AEs if they worsen after starting treatment. Abnormal laboratory values or test results constitute AEs only if they induce clinical signs or symptoms, are considered clinically significant, or require therapy.

The occurrence of AEs should be sought by non-directive questioning of the patient at each visit during the study. Adverse events also may be detected when they are volunteered by the patient during or between visits or through physical examination, laboratory test, or other assessments. All Grade 3 or 4 AEs and all SAEs regardless of grade, must be recorded on the AE CRF with the following information:

- 1. the severity grade (3 or 4 AEs and all SAEs regardless of grade)
- 2. its relationship to HDI or PEG IFN therapy (suspected/not suspected)
- 3. its duration (start and end dates or if continuing at final exam)

All adverse events should be treated appropriately. Treatment may include one or more of the following: no action taken (ie, further observation only); treatment dosage adjusted/temporarily interrupted; treatment permanently discontinued due to this adverse event; concomitant medication given; non-drug therapy given; patient hospitalized/patient's hospitalization prolonged. The action taken to treat the adverse event should be recorded on the AE CRF.

Once an adverse event is detected, it should be followed until its resolution or until it is judged to be permanent, and assessment should be made at each visit (or more frequently, if necessary) of any changes in severity, the suspected relationship to the treatment, the interventions required to treat it, and the outcome.

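### Protocol 9.1 and the SAP use different denominators for the primary compliance endpoint, and under the SAP's a dose held by the physician appears to count as not taken

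*Protocol*

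**What the plan says.** All statements of the primary outcome count doses, but they do not agree on what the count is divided by.

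- Protocol section 9, Primary outcome: "compliance with HDI and PEG IFN (percentage of doses taken as recorded in patient diaries". No denominator is given. A between-group difference of 30% is called clinically relevant.
- Protocol section 9.1: the percentage of doses taken is judged against what the physician prescribed over the treatment period.
- Protocol section 6.8 (section 3 is similar): "Patients will complete drug administration diaries to track compliance with the recommended dosing schedule".
- SAP, primary outcome: the percentage is based on a fixed total of required doses across 53 weeks. "We reported frequencies and percentages per week and an overall percentage of doses taken at the end of 53 weeks", and that overall percentage is the one tested.

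The protocol expects doses to be changed or withheld. Section 3: "Any dose adjustments based on toxicities will be made according to investigator judgment and the package insert for each product". Section 5.1: "The HDI and PEG IFN dose may modified per institutional dosing guidelines". The questionnaire footnotes to Tables 2 and 3 foresee a held or changed dose, and section 7.1 lists adjustment or temporary interruption among the possible responses to an adverse event. Neither document says how a held or reduced dose is scored.

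**The concern.** A patient who takes every dose the physician allows is compliant in the ordinary sense. If the physician holds some doses for toxicity, section 9.1 read naturally leaves that patient at 100%. The SAP's fixed total keeps the held doses in the denominator and so lowers the score. One diary then yields two different values of the primary endpoint.

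The stated objective is compliance with administration of the two drugs. HDI and PEG IFN differ in route and frequency, and treatment is chosen rather than randomized, so there is no reason to assume equal hold rates. A difference between arms on the SAP measure could reflect physicians' holds, and a real difference in patients' behaviour could be masked by them. The result is meant to help decide whether a bigger study should follow, so readers need to know which of the two it describes.

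This point concerns patients still on treatment. Doses falling after a permanent stop are a separate matter.

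**Working it through.** The plan has no figure to reproduce: neither document states the required-dose total per arm, and the sample size was not calculated. The check compares the two denominators on the Table 1 schedule.

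**Inputs from Protocol Table 1, over 52 weeks**
- HDI: induction 5 × 4 = 20 doses; maintenance 3 × 48 = 144 doses; total 164.
- PEG IFN: induction 8 weekly doses; maintenance 52 − 8 = 44 weekly doses in the study year; total 52.

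**Assumption, not in the documents:** a fraction h of maintenance doses is held by the physician and every other dose is taken. Values of h from 25% to 67% are shown for illustration only.

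**Formulas**, with I induction and M maintenance doses:
- SAP score = (I + (1 − h)M) / (I + M)
- Section 9.1 score = (I + (1 − h)M) / (I + (1 − h)M) = 100%
- Gap = hM / (I + M)

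| Maintenance doses held | HDI, SAP score | PEG IFN, SAP score | Either arm, section 9.1 |
|---|---|---|---|
| 25% | 128/164 = 78.0% | 41/52 = 78.8% | 100% |
| 33% | 70.7% | 71.8% | 100% |
| 50% | 92/164 = 56.1% | 30/52 = 57.7% | 100% |
| 67% | 41.5% | 43.6% | 100% |

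For one patient, the gap between the two definitions at h = 50% is 43.9 points (HDI) or 42.3 points (PEG IFN). It passes 30 points when h exceeds 0.30 × 164/144 = 34.2% (HDI) or 0.30 × 52/44 = 35.5% (PEG IFN).

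**53 weeks instead of 52.** Table 1 gives HDI 4 + 48 = 52 weeks, whereas the SAP counts 53. Extending each schedule by one week gives 167 HDI doses and 53 PEG IFN doses. At h = 50% the SAP scores become 93.5/167 = 56.0% and 30.5/53 = 57.5%. The choice hardly matters here, but the totals used should be stated.

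**Arm level.** If h is the mean hold rate in an arm, each 10% of maintenance doses held lowers the SAP score by 10 × 144/164 = 8.8 points (HDI) or 10 × 44/52 = 8.5 points (PEG IFN). With no patient-missed doses in either arm, the artefact between arms is 0.878 × (HDI hold rate) − 0.846 × (PEG IFN hold rate):
- equal hold rates of 25%: 22.0 − 21.2 = 0.8 points;
- assumed rates of 30% (HDI) and 10% (PEG IFN): 26.3 − 8.5, about 17.9 points;
- a 30-point artefact needs a hold rate of about 34% to 35% in one arm and none in the other.

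**The case against.** **The protocol already has the right definition.** Section 9.1 refers to the physician's prescription, so a held dose need not count against the patient. That stands for the protocol. It does not settle the matter, because the SAP describes the analysis reported and uses another denominator. Neither text states a rule for held doses, so both readings are the natural ones rather than certain ones.

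**A reduced dose scores as fully taken.** A reader might infer that this is also an error, since patients on reduced and full doses can score alike. The documents do not support that. The objective is compliance with administration, and taking a prescribed reduced dose is compliance. Amount of drug received is a different quantity.

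**The gap exceeds the 30% threshold.** A reader might set the 42 to 44 points against the plan's 30%. That comparison fails: the gap is between two scorings of one patient at an assumed 50% hold rate, while the 30% is a difference between groups.

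**Nothing records who withheld a dose.** This would also go too far. Section 7.1 says "The action taken to treat the adverse event should be recorded on the AE CRF", although that form takes only Grade 3 and 4 events and serious events. Section 6.9 has interruptions for pregnancy recorded on the CRFs. The diary form is not in the documents and may capture amounts or reasons. What can be said is that no planned analysis separates held from missed doses. The CCSQ domain "Reasons for non-compliance" in section 6.7.1 has no matching item on the form in Appendix 13.1, but the CCSQ is not a source for this endpoint.

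**This is a pilot with exploratory testing.** True, and it limits how much weight any result carries. It does not remove the need for one definition of the primary endpoint.

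**Conclusion.** The concern holds as a conflict of denominators. Sections 6.8 and 9.1 and the SAP give three references for the same percentage. On its natural reading, the SAP's fixed total scores a physician-held dose as not taken, and section 9.1 does not. The SAP result is then closer to treatment received than to patient compliance.

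The size is conditional because the documents report no hold rate. For a single patient the two definitions differ by 21 to 22 points with a quarter of maintenance doses held and by 42 to 44 points with half held. Between arms, the artefact is under 1 point if both hold a quarter and grows by 8.5 to 8.8 points for each additional 10% of maintenance doses held in one arm only. No between-arm bias of a particular size can be claimed from the documents. The figures rest on the Table 1 schedule over 52 weeks and on all doses that were not held being taken.

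**What to change.** 1. Reconcile Protocol sections 6.8 and 9.1 and the SAP on one denominator, with a written scoring rule for held and reduced doses.
2. Report on-treatment compliance as doses taken divided by doses not held by the physician, which is the natural reading of section 9.1. Keep the SAP's required-dose percentage beside it, labelled as treatment received.
3. State the required-dose total for each arm and how 53 weeks maps to Table 1.
4. From existing diaries, CRFs and source notes, report by arm the percentages of doses held by the physician, reduced, missed by the patient, and of unknown reason. Amount received relative to Table 1 is an optional descriptive addition.
5. If the reasons cannot be recovered, limit the conclusion to doses received and do not describe it as patient compliance.

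The cost is SAP wording plus a review of existing records, with up to 164 scheduled doses per HDI patient across 5 to 10 centers. The unknown category may be sizeable and may differ by arm, since the SAP reports widespread missing data that did not look random. Nothing here changes a dose or a clinical rule.
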